1.2 Rationale

ApoPharma Inc. is currently conducting an 18-month trial, TIRCON2012V1, to assess the safety and efficacy of deferiprone in patients with PKAN. In that study, a planned 90 participants are being randomized in a 2:1 ratio to receive either deferiprone oral solution or placebo. Patients are scheduled to undergo weekly monitoring of absolute neutrophil count (ANC) and to undergo safety and efficacy assessments at Months 1.5, 3, 6, 12, and 18.

Patients who complete TIRCON2012V1 will be invited to enroll in the current study, in which all participants will receive deferiprone. Participants will thus receive deferiprone for a total of either 1.5 years or 3 years, depending on which treatment was assigned in the earlier study. The long-term data obtained will enable a better understanding of the use of deferiprone in this patient population.

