3.1 Study Design

Study TIRCON2012V1-EXT is an 18-month, multi-center, single-arm, open-label extension of study TIRCON2012V1. In the initial study, patients with a diagnosis of PKAN were being randomized in a 2:1 ratio to receive 18 months of treatment with either deferiprone or placebo, respectively. All participants who completed TIRCON2012V1 were offered the opportunity to continue in the extension study, with the final visit of the initial study being considered Visit 1 of the extension study. Patients who had been randomized to receive deferiprone in study TIRCON2012V1 continued to receive deferiprone in the extension study, while those who had been randomized to receive placebo were switched to deferiprone. Since the initial study were still in progress at the time that the first patients entered the extension study, patients and study staff remained blinded until the initial study was over as to which product was received for the previous 18 months.

In the TIRCON-EXT study, patients will have their hematology blood counts monitored weekly, and will return to the study site at 6 months (Visit 2), 12 months (Visit 3), and 18 months (Visit 4) for assessments of safety and efficacy.

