extension study. Continuous variables will be compared by paired t-tests while proportions by McNemar's test. If statistically significant imbalances are detected, they will be adjusted accordingly for the comparison of changes in BAD and PGI-I between the initial study and the extension study by using a MMRM model approach that is consistent with the analysis of these two efficacy measures in the initial study. The MMRM model is specified below.

The MMRM model will be applied to non-imputed data from the observed cases (OC) data set. Let y_i denote the vector of n_i continuous post-baseline measurements observed for study patient i . Each response (i.e., each element of y_i) will be defined as the patient's score at that occasion minus the baseline score.

The model will assume that the distribution of y_i is multivariate normal,

$$y_i \sim N(X_i\beta, \Sigma_i),$$

where X_i is a design matrix of dimensions $n_i \times p$, β is a vector of coefficients of length p , and Σ_i is an $n_i \times n_i$ covariance matrix.

The MMRM model will include baseline value of the outcome as a covariate and treatment group as the main factor in the model. A change in DBS settings or use of medications that have the potential to affect dystonia symptoms during the study may confound the treatment effect assessment (named outcome impacting medication use hereafter) for DFP vs. placebo between the initial study and the extension study for patients who were on placebo in the initial study. Hence, both variables will also be included in the MMRM model as visit-dependent covariates.

The visit-dependent covariate for DBS settings change is defined as follows: for patients with DBS at enrollment, if there is any DBS setting change since the previous visit, it will be coded as 'DBS Setting Change' for the current visit or 'No DBS Setting Change' otherwise. For example, if a patient has a DBS setting change between the outcome assessment dates at month 6 visit and month 12 visit, it will be coded as 'DBS Setting Change' for month 12 visit in the model. For those patients without DBS at enrollment, it will be coded as 'No DBS'. A discrete variable, DBSCHG, with three categories will be included in the MMRM model.

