The visit-dependent covariate for the outcome impacting medication use will be defined according to whether the patient is on a regular dosing regimen or on a PRN (as needed) dosing regimen between two visits. For patients treated on a regular dosing regimen, if there is a dose change or starting of new medication since the previous visit, it will be coded as 'Yes' for the current visit and the future follow-up visits or 'No' otherwise in the model. For patients who do not use any outcome impacting medication, it will be coded as 'No'.

For patients on a PRN (as needed) dosing regimen, the visit-dependent covariate will be defined according to the treatment impact period in the following table.

Medication	Treatment impact period
Baclofen	30 days
Trihexyphenidyl	30 days
Clonazepam	30 days
Tizanidine	30 days
Botox	60 days
Tetrabenazine	90 days

If the PRN drug is started within the treatment impact period prior to the assessment date of an outcome for a visit, it will be coded as ‘Yes’ for that visit. If the drug is started outside this time window but is not interrupted within this period, it will also be coded as ‘Yes’ for that visit. Under other conditions, it will be coded as ‘No’ in the model. A binary variable for the outcome impacting medication use, RESMED, will be included in the MMRM model.

The frequency of PRN drug or rescue medication use between two outcome assessment dates of current visit and the previous visit will also be included in the MMRM model as a quantitative visit-dependent covariate, NDRUG, for the current visit.

The MIXED procedure in SAS will be used for the MMRM model analysis. Data within each patient at different visits will be considered repeated measures. AR(1) (autoregressive of order 1) covariance structure will be used to model the correlation between repeated measures within the same patient and Kenward and Roger’s method will be used to estimate the denominator degrees of freedom. The 95% confidence interval (CI) for the difference between the two treatments will be calculated by the LSMEANS statement.

A sample SAS code for the MMRM model is presented in the box below:

```
proc mixed;
  class TREAT USUBJID VISIT DBSCHG RESMED;
  model CHG=TREAT VISIT TREAT*VISIT BASE DBSCHG RESMED
  NDRUG/solution ddfm=kr;
  repeated VISIT/ subject=USUBJID type=ar(1);
  lsmeans TREAT*VISIT / diff cl;
run;
```

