where TREAT is the indicator variable for treatment group (DFP vs. Placebo), USUBJID represents the patient ID, VISIT is the discrete variable representing the scheduled study visit after the baseline visit, DBSCHG is the discrete variable with three categories for

DBS settings change (DBS Setting Change, No DBS Setting Change, No DBS), RESMED is the binary variable for outcome impacting medication use (Yes vs. No), CHG is the change in value of efficacy outcome from baseline to the scheduled visit, BASE is the baseline value of efficacy outcome, and NDRUG is the frequency of PRN drug or rescue medication use.

PGI-I is already a measurement of change from baseline and thus will be used directly as the outcome variable and baseline BAD score will be included as the baseline value in all models.

McNemar's test will be used to compare the proportion of responders in the initial study with the proportion of responders in the extension study.

For all patients who were on DFP in both studies, the longitudinal response profile for BAD score will be explored by a MMRM model with time modelled as a continuous variable.

For this model, AR(1) (autoregressive of order 1) covariance structure will be used to model the correlation between repeated measures within the same patient and Kenward and Roger's method will be used to estimate the denominator degrees of freedom.

A sample SAS code for this MMRM model is presented in the box below:

```
proc mixed;  
  class USUBJID VISIT;  
  model BAD= TIME /solution ddfm=kr;  
  repeated VISIT/ subject=USUBJID type=ar(1);  
run;
```

where USUBJID represents the patient ID, VISIT is the discrete variable representing the scheduled study visit after the baseline visit, BAD is the value of BAD score at each time point, and TIME is the time in months at each time point corresponding to each visit.

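### The DBS covariate in the placebo-switcher MMRM lapses after one visit although the outcome is cumulative, so imbalance in earlier reprogramming stays largely unadjusted at Visit 4, in either direction

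*SAP*

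**What the plan says.** The MMRM in SAP section 4 compares the placebo period with the deferiprone period in patients who had placebo in the initial study. Under SAP sections 3.5 and 4 it is used only if a significant imbalance between the periods is found in DBS changes, outcome-impacting medication, or PRN/rescue use. Otherwise a paired t-test is used.

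- **DBS covariate (DBSCHG).** For patients with DBS at enrolment, "if there is any DBS setting change since the previous visit, it will be coded as" a setting change for the current visit, and as no change otherwise. The worked example reads "if a patient has a DBS setting change between the outcome assessment dates at month 6 visit and month 12 visit"; it assigns the flag to month 12 and does not mention month 18.
- **Response.** Each element is the patient's "score at that occasion minus the baseline score". The key to the SAS code repeats this: "CHG is the change in value of efficacy outcome from baseline to the scheduled visit".
- **Model.** The statement begins "model CHG=TREAT VISIT TREAT*VISIT BASE DBSCHG RESMED". DBSCHG is a single additive class effect, with no lagged or cumulative DBS term.
- **Medication covariate (RESMED).** For regular regimens, a dose change or new drug is coded as present "for the current visit and the future follow-up visits".

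The Visit 4 contrast from this model is reported in Table 14.2.2.9.

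**The concern.** The SAP says that a DBS setting change may confound the comparison of deferiprone with placebo, and it adds DBSCHG for that reason. A new setting normally stays in force until it is changed again, much like a new regular dose, and its effect on dystonia stays in every later change from baseline. The SAP carries the medication change forward but lets the DBS change lapse, and gives no reason for the difference.

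A patient reprogrammed at month 5 and left on the new setting is coded as unchanged at months 12 and 18. This has two consequences. The month-18 contrast is not adjusted for that patient's change. In addition, the later visits, which still carry the effect, join the no-change reference category and pull the DBSCHG coefficient towards zero. When DBS imbalance is what triggers the model, the covariate meant to remove that imbalance misses most of it at the visit that is reported.

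**Working it through.** The documents state no sample size, effect size or DBS figure for this comparison, so there is no planned number to reproduce.

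**1. Look-back at Visit 4.** Extension visits are at "6 months (Visit 2), 12 months (Visit 3), and 18 months (Visit 4"). In the initial study, patients "undergo safety and efficacy assessments at Months 1.5, 3, 6, 12, and 18" (protocol section 1.2). The last interval is months 12 to 18 in both periods, so coverage is (18 - 12)/18 = 6/18 = 33%. This is nominal: a missed month-12 visit could lengthen it if the previous visit means the last one attended.

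**2. Share of reprogrammed patients flagged at month 18.** Assume an independent chance p of a change in each 6-month interval. Among DBS patients with at least one change, the share flagged at month 18 is p / (1 - (1 - p)^3):
- p = 0.1: 0.1/0.271 = 37%
- p = 0.3: 0.3/0.657 = 46%
- p = 0.5: 0.5/0.875 = 57%

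**3. Bias by hand.** From SAP section 3.2, 24 switchers. Assumed: 12 have DBS; 10% of these have a setting change in the placebo period and 60% in the deferiprone period; a change lowers BAD by a lasting 3 points; deferiprone is inert.
- Unadjusted bias = share with DBS x difference in change rates x effect = 0.5 x (0.60 - 0.10) x (-3) = -0.75.
- If changes are spread evenly over the three intervals, two-thirds precede month 12. Even with the coefficient known exactly, 2/3 x (-0.75) = -0.50 would remain.
- Dilution of the coefficient leaves somewhat more than that.

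**4. Bias by simulation.** Three visits per period, both periods in the same patients, residual SD 2, AR(1) correlation 0.6 within period, a change equally likely in each interval. BASE, RESMED and NDRUG are omitted and errors are independent between periods. Bias is in the month-18 deferiprone-minus-placebo contrast (true value 0) under the as-written coding:

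| DBS patients | Changed, placebo vs deferiprone period | Lasting effect | Bias |
|---|---|---|---|
| 12 | 10% vs 60% | -3 | -0.60 |
| 12 | 35% vs 35% | -3 | 0.01 |
| 12 | 60% vs 10% | -3 | +0.59 |
| 12 | 10% vs 60% | -1 | -0.16 |
| 5 | 10% vs 60% | -3 | -0.21 |

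In the first row, 0.60/0.75 = 80% of the unadjusted bias remains. Carrying the flag forward brings it to about 0.

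**5. Timing.** A second set-up (half with DBS, SD 3, correlation 0.7, 200 patients per run to reduce noise) placed changes mostly early in the deferiprone period: 50%, 30% and 5% by interval, against 5% in each placebo interval. The as-written coding then gave -0.82, the same as no DBS adjustment.

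**6. If the effect does not last.** When the effect is gone by the next visit, as-written coding gives -0.01 and carry-forward gives +0.34. The result in step 4 therefore depends on persistence.

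**The case against.** A reader might infer that earlier reprogramming is credited to deferiprone. The documents do not support a direction. The same rule applies in the placebo period, so uncoded early changes there stay in the placebo estimate; the sign follows whichever period has more of them, and equal rates cancel.

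A reader might also infer that the imbalance test and the Overall row of Table 14.2.2.8 share the defect. No text says that either uses the last-interval rule, so neither is part of this point.

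The case for leaving the coding alone has five parts.

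- **Inputs.** DBS prevalence, change rates and effect size are all assumed. Protocol section 5.1 asks patients to make every effort to keep settings stable, so a 60% change rate may be high. This stands, and is why a range is shown.
- **Trigger.** With 12 DBS patients and 10% versus 60% changed, an exact McNemar test on DBS changes is significant in about 54% of trials, and an asymptotic one in about 74%. With 5 DBS patients the exact test cannot reach 0.05, since 2 x 0.5^5 = 0.0625. Medication or PRN imbalance could still trigger the model, but DBS need not then be imbalanced. This limits how often the defect bites; it does not correct the model once triggered.
- **Persistence.** Carry-forward looks unbiased in step 4 because the data were generated with a lasting effect. This stands.
- **Inheritance.** Protocol section 9.4.1.3 and SAP section 4 require consistency with the initial-study model, whose plan is not available here. The coding may come from there, which argues for retaining it as a sensitivity analysis.
- **Safeguards.** The PP population excludes patients with DBS setting changes, and Table 14.2.2.8 shows changes by visit and period. These would reveal an early imbalance and give a partial check in a smaller subset. The ITT population is primary, though, and the table list has no PP version of Table 14.2.2.9.

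**Conclusion.** The point holds as a mismatch between covariate and outcome. DBSCHG lapses after one visit, the response accumulates from baseline, and the parallel medication covariate is carried forward. At Visit 4 the flag nominally covers 6 of 18 months in each period. If the MMRM is triggered and early reprogramming differs between periods, most of its lasting effect stays in the contrast.

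Under the stated assumptions the residual is about 0.6 points on the 0 to 32 BAD scale with 12 DBS patients and a lasting 3-point effect. It is about 0.2 points with a 1-point effect or only 5 DBS patients, and nil with equal rates. The direction is not predictable from the documents. The reach is limited to DBS patients, to former placebo patients, and to a conditional analysis of secondary endpoints in an open-label safety extension. The correction is worth making because it is cheap and because removing this confounding is the covariate's stated purpose.

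**What to change.** In SAP section 4, define DBSCHG so that a setting change is coded for the current visit and all later visits of the same study period, mirroring the regular-regimen rule for RESMED. Reset the flag at extension Visit 1, so that the deferiprone period starts from its own baseline. Keep the as-written coding as a sensitivity analysis of Table 14.2.2.9, and state that the main coding assumes the effect of a setting change persists.

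The cost is one sentence, a changed derivation and one extra model run. No new data are needed: protocol section 7.2.3.4 already collects DBS changes, and Listing 16.2.9.4 reports them. The downside is reliance on the persistence assumption, which the sensitivity analysis exposes.

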5.1 Visit Procedures

Visit 1 (Week 0)

This visit is the Month 18 visit of TIRCON2012V1: i.e., for patients who choose to continue on, the last visit of the initial study is considered the first of the extension study. For patients who had been on placebo and will now be receiving deferiprone for the first time, the data obtained at this visit will be treated as the baseline measures for TIRCON2012V1-EXT.

The following procedures will be done:

- Explain the extension study to the patient and/or authorized legal representative, and obtain written informed consent/assent
- Confirm eligibility criteria
- Review medical history
- Collect information about concomitant medications
- Ask patient about the use of any of the medications listed in [Appendix 3](#) or any other medication that has the potential to affect dystonia symptoms (e.g., spasticity, muscular rigidity, and parkinsonism), as follows:
 - If patient has been on a regular dosing regimen of any of these medications since the start of study TIRCON2012V1, verify that the regimen has been stable
 - If patient has been taking any of these medications on a PRN (as needed) basis since the start of study TIRCON2012V1, verify that treatment was interrupted prior to the current visit according to the following timelines:

Medication	Treatment interruption period prior to current visit
Baclofen	30 days
Trihexyphenidyl	30 days
Clonazepam	30 days
Tizanidine	30 days
Botox	60 days
Tetrabenazine	90 days

- If patient has a DBS system or Baclofen pump in place, verify that the DBS stimulation parameters or pump settings have been stable, as confirmed by the investigator

- Collect blood samples for the following assessments:
 - Hematology
 - Blood chemistry
 - Pregnancy testing for all sexually active females of childbearing potential (if applicable; in cases where the investigator determines there is no reasonable risk of pregnancy because of significant incapacity, pregnancy testing will not be performed)
- Collect a urine sample for urinalysis
- Measure vital signs, weight, and height
- Perform a 12-lead ECG
- Conduct contraceptive counseling for sexually active patients
- The following must be performed by a qualified investigator or a qualified delegate:
 - Conduct a physical examination
 - Record administration of the BAD in a standardized manner on videotape, and transmit tape to the evaluation center
- Verify dosage of study medication
- Dispense a 6-month supply of study medication

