APPENDIX 3: LIST OF RESCUE MEDICATIONS

Rescue medication is defined as a newly prescribed medication or a change in dosage of a currently prescribed medication that has the potential to have an effect on dystonia symptoms and is provided because of a worsening of the patient's condition.

The use of rescue medication should be limited to circumstances judged as absolutely necessary by the investigator. Any use of a rescue medication must be documented, including the reason. If a patient uses rescue medication for more than 2 events, the investigator should notify the sponsor to discuss the patient's continued participation in the study.

Rescue medications for dystonia include, but are not limited to, the following:

- Baclofen
- Trihexyphenidyl
- Clonazepam
- Tizanidine
- Tetrabenazine
- Botox

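### On its ordinary wording, the SAP's PRN rule for RESMED codes No for a listed dystonia drug started before the impact period and stopped inside it, although the protocol washout of the same length was not met

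*SAP*

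**What the plan says.** SAP Section 4 introduces RESMED as a visit-dependent covariate. For PRN users, "the visit-dependent covariate will be defined according to the treatment impact period in the following table". The table gives 30 days for baclofen, trihexyphenidyl, clonazepam and tizanidine, 60 days for Botox and 90 days for tetrabenazine. Three sentences then fix the coding:

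- "If the PRN drug is started within the treatment impact period prior to the assessment date of an outcome for a visit, it will be" set to Yes.
- "If the drug is started outside this time window but is not interrupted within this period, it will also be coded as" Yes.
- "Under other conditions, it will be coded as" No.

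Protocol Section 5.1 lists the same six drugs with the same 30, 60 and 90 days as interruption periods before a visit. For PRN users, site staff are to "verify that treatment was interrupted prior to the current visit according to the following timelines". There the drug is to be withheld for the whole listed time before the assessment.

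The SAP uses medication coding in three places, all for patients who received placebo in the initial study:

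- Table 14.2.2.8 tabulates outcome-impacting medication use as Yes or No at each visit and overall.
- The incidence of that use is compared between the two studies, with McNemar's test for proportions. "If statistically significant imbalances are detected, they will be adjusted accordingly for the comparison of changes in BAD and PGI-I", by an MMRM. Otherwise a paired t-test is used (SAP Section 3.5).
- RESMED is a covariate in that MMRM.

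The model also contains NDRUG: "The frequency of PRN drug or rescue medication use between two outcome assessment dates of current visit and the previous visit will also be included".

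**The concern.** RESMED exists to mark assessments at which a symptomatic drug may have influenced the BAD or PGI-I score. The impact periods match the protocol washout, so one would expect RESMED to be No when the washout was met and Yes when it was not. The second PRN sentence does not secure this. It turns on whether the drug was interrupted within the period, and a drug stopped two days before the visit was, in ordinary English, interrupted within the period. It then meets neither Yes condition and falls to the residual No.

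The consequence reaches beyond one covariate. The imbalance comparison decides between a paired t-test using the last observed data and an MMRM on observed cases, so both the method and the handling of missing data can depend on how a few visits are coded. If the MMRM is run, a miscoded RESMED leaves some confounding by symptomatic drug in the placebo-period versus deferiprone-period contrast.

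**Working it through.** The plan states no figure to reproduce. The check takes the rule as written, applies it to each possible pattern of start and stop dates, and compares the result with the protocol washout.

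**Inputs.** W is the impact period (30, 60 or 90 days; SAP Section 4), equal to the interruption period in Protocol Section 5.1. Let s and e be the number of days before the assessment on which the drug was started and stopped, with e = 0 if it is ongoing. For a drug started before the window (s > W), the washout is not met if e < W.

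**Three readings of the second sentence** (the first makes every s ≤ W a Yes):

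- R1, strict stop date: Yes unless the stop date lies in the window (0 < e ≤ W).
- R2, still in use: Yes only if e = 0.
- R3, the protocol's sense: Yes unless the drug was withheld for the whole window, that is Yes if e < W.

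**Result, the same for W = 30, 60 and 90:**

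| Pattern | Washout | R1 | R2 | R3 |
|---|---|---|---|---|
| Started inside, stopped inside | not met | Yes | Yes | Yes |
| Started inside, ongoing | not met | Yes | Yes | Yes |
| Started before, ongoing | not met | Yes | Yes | Yes |
| Started before, stopped inside | not met | **No** | **No** | Yes |
| Started before, stopped before the window | met | **Yes** | No | No |

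Bold entries disagree with the washout.

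**Fourth row in full.** With the start before the window, the breaching stop days are e = 1 to W − 1, so 29, 59 or 89 days. R1 and R2 code No on 29 of 29, 59 of 59 and 89 of 89. R3 codes No on 0 of 29, 0 of 59 and 0 of 89.

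**Example.** PRN baclofen (W = 30), started 60 days before the visit and stopped 1 day before it, is No under R1 and R2 and Yes under R3. Stopped 40 days before the visit instead, so that the washout was met, it is Yes under R1 and No under R2 and R3.

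**Sensitivity of the imbalance test.** SAP Section 3.2 gives 24 former placebo patients, and Section 3.6 a two-sided 0.05 level. The SAP does not say whether McNemar's test is asymptotic or exact. As an illustration, let all b discordant pairs fall on one side:

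- Asymptotic: the statistic is b²/b = b on 1 degree of freedom. b = 3 gives p = 0.083; b = 4 gives p = 0.046.
- Exact: p = 2 × 0.5^b. b = 5 gives p = 0.063; b = 6 gives p = 0.031.

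In either form, recoding one patient near the threshold changes whether the test is significant. The SAP does not name RESMED in this comparison. I assume that it uses the same Yes/No coding, because the Table 14.2.2.8 shell has that variable with those two categories.

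**The case against.** The strongest reply is that the sentence is loosely worded but its meaning is clear from its source. The drugs and day counts are those of the protocol's interruption table, where interrupted means withheld for that time. Read so (R3), the rule codes every pattern correctly. The odd result of R1 for a compliant patient also suggests poor wording more than a deliberate rule. This stands as far as intent goes. It does not settle the coding: R3 needs the word within to mean throughout, and a programmer working from the SAP could defend any of the three readings.

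A second reply is that NDRUG, in the same model and separately tested for imbalance, already counts PRN and rescue use. It offsets the error only in part. It covers the whole interval since the previous visit, about six months in the extension, and does not separate use just before the video from use months earlier. The per-protocol analysis excludes patients with changes in dystonia-relevant medication, but that is a patient-level exclusion and does not correct RESMED in the ITT model.

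Three stronger readings are tempting, and the documents do not support them:

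- *All washout breaches count as unexposed.* Three of the four breach patterns in the table are Yes under every reading.
- *A percentage of breaches is miscoded in this trial.* For continuous courses of fixed length D with uniformly distributed starts, the share coded No under the stop-date readings is min(D, W)/(W + D): for example 14/(30 + 14) = 32% for D = 14 and W = 30, or 30/(30 + 30) = 50% for D = 30 and W = 30. These are hypothetical courses. The documents give no frequency of PRN use or of breaches, and stop dates would not be independent of visits when interruption is required beforehand.
- *PRN drugs outside the six are wrongly coded No.* Protocol Appendix 3 is open-ended ("Rescue medications for dystonia include, but are not limited to, the following"), and the SAP's rescue-medication shell names diazepam. For such a PRN drug the SAP gives no impact period, so its coding is undefined more than wrong.

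**Conclusion.** The concern holds for one pattern. On the ordinary wording, a listed PRN drug started before the impact period and stopped inside it is coded No, although the washout was not met. Under the strict stop-date reading, a compliant patient is also coded Yes. The defect is an ambiguous definition of a prespecified variable, and the resulting dataset depends on who programs it.

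Its reach is limited to at most 24 patients, secondary endpoints of an open-label safety study, and a model that runs only if an imbalance test is significant. The comparison itself is planned in every case, so the coding can matter even if the MMRM is never fitted. The size and direction of any bias cannot be computed from the documents. The correction is worth making because the rule is explicit, feeds a choice of method and is easily put right.

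**What to change.** Replace the PRN coding sentences in SAP Section 4 with:

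> RESMED = Yes for a visit if the PRN drug was used on any day within its treatment impact period before the assessment date; RESMED = No only if it was withheld for the whole period.

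Apply this identically to the placebo and deferiprone periods, in Table 14.2.2.8, in the imbalance test and in the MMRM. In the check above this is R3: no breaching stop day is coded No, and a patient who stopped before the window is coded No.

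The cost is a short change of wording. Protocol Section 7.2.3.4 already collects start and stop dates in the extension. Three cautions apply. Somewhat more visits may be flagged as affected. Where a PRN record is left open, documented interruptions must be used, or a patient who withheld the drug would be coded Yes. The placebo-period values come from the initial study, whose data collection and analysis plan are not among these documents; since the SAP wants the model consistent with that study's analysis, any departure in coding should be stated.

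The change leaves the clinical washout rule untouched. It does not supply an impact period for PRN drugs outside the table, because the documents offer no basis for choosing one.
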